Short et al describes a quantifiable anatomical explanation for incomplete or failed anaesthesia from FNB or FICB in patients with #NOF. Several studies demonstrate that the FN block and FICB do not reliably block the obturator nerve or the lumbar plexus [16-22]. Distally, the high articular branches of the FN and AON are consistently located between the anterior inferior iliac spine and the iliopubic eminence [15]. The articular branches of the ON are located close to the inferomedial acetabulum. [15,23]. Subsequently the pericapsular nerve group block (PENGB) was designed to target the articular branches of the FN and AON by infiltrating the sub-psoas space at the level of the iliopubic eminence [23]. A case series of 5 consecutive patients with #NOF at Toronto Western Hospital was published in November 2018 and demonstrated the feasibility and efficacy of this block [23]. There is no published data describing the duration of analgesia provided by the PENG block.

The PENGB has subsequently been adopted by several practitioners at Lismore Base Hospital for the treatment of #NOF. We believe there is a study ongoing in peri-operative patients comparing PENGB to FICB in Toronto. We are not aware of any research into the utilisation of the PENGB in the emergency department setting. Searches of multiple study registries reveal no ongoing trials.

A retrospective study of patients that received regional anaesthesia for # NOF at LBH in the first 4 months of 2019 was performed. This data included 40 patients that received regional anaesthesia in ED, 6 of whom received a PENG block.

In this audit, patients' total opioid requirements from time of block to time of operation were recorded and converted to oral morphine equivalents using the ANZCA Faculty of Pain Opioid Calculator.

This audit found that patients receiving PENG blocks required fewer opioids pre operatively (mean = 22.67 mg) than did patients who did not receive a PENG block (FIB mean = 26.15 mg and FNB mean = 30.90 mg). Of note, patients receiving PENG blocks required fewer opioids in the 0-6 hours period immediately post block (mean = 3.00 mg) than did patients who did not receive a PENG block (FIB mean = 6.38 mg and FNB mean = 9.10). These results were not statistically significant ($p = 0.5$). The null hypothesis was retained. One adverse event relating to PENG blocks was documented in the records (failed block).

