All patients presenting to Lismore Base Hospital with fractured neck of femur (#NOF) are placed on the NOF pathway. The pathway suggests that patients on the NOF pathway should receive regional anaesthesia (nerve block) within 30 minutes of arriving at the Emergency Department. The nerve block performed will be determined by the treating clinician.

Inclusion and Exclusion Criteria

Inclusion Criteria

1. Adult patients (>18 years) presenting to Lismore Base Hospital Emergency Department with radiologically confirmed #NOF. The neck of femur fractures include:
 - a. Sub-capital fracture
 - b. Surgical neck fracture
 - c. Intertrochanteric fracture
 - d. Peritrochanteric fracture
2. The patient receives a nerve block for their fractured neck of femur in the Lismore Base Hospital Emergency Department
3. The nerve block may occur before or after the radiological confirmation of diagnosis

Exclusion Criteria:

1. Regional anaesthesia not provided in the Lismore Base Hospital Emergency Department
2. Allergy to amide local anaesthetics
3. Infection of the skin overlying at the overlying the site of potential nerve block
4. The patient has already received a nerve block for this fracture prior to arrival in at Lismore Base Hospital
5. Other reason at the discretion of clinician/s
6. Femoral shaft fracture

Block Standardisation

As this is an observational study, intervention is not dictated by the study, but is at the discretion of the treating physician. However, there have been efforts to standardise aspects of the care provided to improve the validity of this observational data.

In accordance with usual standards of practice:

- All nerve blocks are to be performed with ultrasound guidance. Needle tip and infiltration should be directly visualised with ultrasound.
- All nerve blocks are to be performed with continuous cardiac monitoring and intravenous access.

Nerve Block Kit:

To encourage standardisation of nerve blocks within hour department a nerve block kit is already in use. It contains:

- 80 mm x 21 gauge Pajunk SonoSpot needle (or alternative needle stocked by the department)
- 0.9% sodium chloride - 1 x 10mL vial
- 20 mL luer lock syringe
- 3 mL luer lock syringe
- Drawing up needle
- 25 gauge 38 mm or 23 gauge 35mm needle for local infiltration
- Dressing kit
- Chlorhexidine 2% in 70% ethanol skin prep solution (30 mL)
- Sterile ultrasound probe cover and gel

Standard Order Set:

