- Treatment in this phase of the patient's journey will be decided by the acute pain service or duty anaesthetist. The investigators will have no influence over which repeat block the patient receives.

Block failure

- Defined as maximum pain score improvement of less than 1.5 out of 10.

Duration of analgesia from nerve block

- End of block effect defined as an increase in pain score to ≤ 1.0 from pre-block pain score in a patient who had a reduction in pain score of > 1.5 at any time.

Opioid Requirement

- Opioid intake will be measured by analysis of the electronic medication chart from the insertion of block until 12 hours have passed, or the patient is checked in to the operating theatre, whichever occurs first.
- This information will be converted to milligrams of oral morphine using the Faculty of Pain Medicine Opioid Calculator

Adverse events

In an effort to detect the incidence of adverse events, the investigators will:

- Perform a keyword search of the “Continuous Doc” feature of the electronic record, after the patient is discharged from the hospital.
 - Keywords:
 - Delirium
 - Sedation
 - Constipation / Constipated
 - Aspiration
 - Naloxone
- Review the electronic medication chart for use of:
 - Naloxone
 - Antibiotics

Surgery Waiting Time:

Time to surgery will be defined as the time from Triage in the Emergency Department to the time of Check In at Operating Theatre for operative fixation.

Data collection on our cohort for the purposes of the primary outcome will cease at the time of check in to the operating theatre or at 12 hours after the insertion of nerve block, whichever is sooner.

Mean, median and longest wait times will be recorded. This information will inform future practice at our hospital.

Data Collection and Storage

Primary Data Recording Methods:

Were discussed above and are summarised here:

- ❑ Documentation in the electronic medical record record (PowerChart / FirstNet / SurgiNet) as is usual practice for all patients treated in the emergency department and those admitted to the hospital
- ❑ Documentation on the paper SPIED Limb Observation Chart [Appendix 6] which is usual practice for patients admitted to the inpatient orthopaedic and surgical ward with fractured neck of femur. The standard chart has been modified for the SPIED study to include pain scores and pain score calculators.

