This project aims to improve understanding of the PENG block and its effects. We aim to publish results, either positive or negative, in a peer-reviewed journal approved by the Australasiaon College of Emergency Medicine and/or at appropriate scientific meetings.

Justice

All patients presenting to our facility with #NOF will be eligible for inclusion in this study. The patient experience of receiving the PENG block is very similar to that of receiving FNB or FICB and a lay-person would unlikely be able to tell the difference. There is no increased burden on patients enrolled nor on those not enrolled.

Beneficence

We believe that all patients present and future will benefit from the standardisation of practice and the establishment of preferred practice within our health service.

Risk

We do not anticipate that this study exposes participants to an increased risk. As outlined above we believe the PENG block conveys safety advantages compared to standard blocks the FNB and FICB. Most important is the physical separation of the site and the tissue plane of infiltration from major blood vessels. This reduces the risk of local anaesthetic systemic toxicity - which is the most serious adverse event associated with regional anaesthesia. Additionally, the nerves targeted and affected by the PENGGB are small, sensory nerves. Any trauma or toxicity to nerves as a result of a PENGGB would have no effect on motor nerves, which provide power to the thigh. Conversely, both the FICB and FNB effect larger motor nerves and any nerve trauma or toxicity can theoretically affect the muscle power in the thigh. We note that there is poor evidence supporting the argument that regional anaesthesia causes clinically significant trauma or toxicity to motor nerves.

Outcomes and Significance

The PENG block is a new therapy with a sound scientific basis and promising preliminary results both in the limited existing literature and our experience delivering this therapy at Lismore Base Hospital. If it is a superior regional analgesic then it follows that the therapy should be superiorly opioid-sparing. As we know, the study population is particularly at risk of complications from opioid analgesia [5-7]. Also, we know that pain (a result of ineffective analgesia) itself is a risk factor for agitation and delirium [reference] [29-33]. It follows that there would be an improvement in patient safety and patient-important outcomes from wider adoption of a superior intervention.

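### Opioid requirement is a milligram amount over unequal observation times, so any difference between blocks in time to theatre within 12 h would show as a difference in opioid use

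*Protocol*

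**What the plan says.** In the protocol, under Secondary Outcomes, the subsection Opioid Requirement sets the collection window as "from the insertion of block until 12 hours have passed, or the patient is checked in to the operating theatre, whichever occurs first". On the unit it says: "This information will be converted to milligrams of oral morphine using the Faculty of Pain Medicine Opioid Calculator". It states no rate per hour, no common window and no adjustment for time observed.

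Opioid requirement has its own subsection, but it is missing from the bulleted list that opens Secondary Outcomes and from the Statistical Analysis section. No summary or test is named for it.

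Allocation is not randomised. Under Study Design, Current Practice: "The nerve block performed will be determined by the treating clinician".

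The subsection Surgery Waiting Time covers waiting separately and gives this definition: "Time to surgery will be defined as the time from Triage in the Emergency Department to the time of Check In at Operating Theatre". Its stated use is descriptive: "Mean, median and longest wait times will be recorded. This information will inform future practice at our hospital". It is not broken down by block and not linked to opioid intake.

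Under Outcomes and Significance, the protocol connects analgesic superiority to opioid use: "If it is a superior regional analgesic then it follows that the therapy should be superiorly opioid-sparing".

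**The concern.** A cumulative amount over a window of patient-specific length mixes two things: how fast opioid is used, and how long the patient is watched. In a randomised comparison the second would balance on average and mainly add noise. Here clinicians choose the block, and nothing in the design keeps block-to-theatre time equal between groups. If one block is given more often to patients who go to theatre early, that group will record less opioid with no better analgesia. The imbalance could as easily run the other way and hide a real saving.

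The planned waiting-time summary would not reveal this, since it is not required by block. It also starts at triage and not at block insertion. That second difference may be small where the pathway's suggested 30 minutes from arrival to block is met.

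At stake is how a secondary result is read, on a theme the protocol uses in its patient-safety rationale. The primary outcome's sample size is not involved.

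**Working it through.** The protocol states no effect size, power or sample size for opioid requirement, so there is no figure of its own to reproduce.

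**1. What the definition implies for one patient.** Observed time W = min(12 h, block to check-in). At a constant rate r, the recorded total is r × W. With r assumed at 1.0 to 2.0 mg/h, W = 6 h gives 6 to 12 mg and W = 12 h gives 12 to 24 mg: a factor of two from observation time alone.

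**2. What it could do to a group comparison.** Inputs: the audit's 0-6 h mean for fascia iliaca block, 6.38 mg, so r = 6.38/6 = 1.063 mg/h in both groups (no block effect). The proportions in theatre at 6 h are assumptions; everyone else is taken as observed for 12 h.
- 10% at 6 h: mean W = 0.1 × 6 + 0.9 × 12 = 11.4 h, total 12.1 mg.
- 30% at 6 h: mean W = 0.3 × 6 + 0.7 × 12 = 10.2 h, total 10.8 mg; 10.2/11.4 = 0.895, an apparent saving of about 11%.
- 50% at 6 h: mean W = 0.5 × 6 + 0.5 × 12 = 9.0 h, total 9.6 mg; 9.0/11.4 = 0.789, about 21%.

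**3. How it depends on waiting time.** A simulation (4,000 runs per row, all inputs assumed except group sizes) used 41 PENG and 125 − 41 = 84 comparator patients, the protocol's early-termination numbers. Both groups used 1.5 mg/h, with between-patient CV 0.6. Time to theatre was lognormal with log-SD 0.5, and totals were compared by a two-sided t-test at 0.05.

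| Median time to theatre, PENG v comparator | Mean time observed | Mean difference in total | False-positive rate |
|---|---|---|---|
| 20 v 20 h | 11.6 v 11.6 h | 0.0 mg | 4.9% |
| 10 v 10 h | 9.4 v 9.4 h | 0.0 mg | 5.8% |
| 20 v 30 h | 11.6 v 11.9 h | −0.5 mg | 5.7% |
| 16 v 20 h | 11.2 v 11.6 h | −0.7 mg | 6.1% |
| 10 v 14 h | 9.3 v 10.8 h | −2.2 mg | 19% |
| 8 v 12 h | 8.2 v 10.2 h | −3.0 mg | 38% |
| 8 v 16 h | 8.2 v 11.2 h | −4.5 mg | 67% |

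Analysed as mg per hour, the false-positive rate was 4.3% to 5.5% throughout. That follows from simulating a constant rate and does not show that mg per hour is safe when the rate changes.

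**4. What the audit says about waits.** Under the same constant-rate model, the audit means imply average waits of 26.15/(6.38/6) = 24.6 h for fascia iliaca block and 30.90/(9.10/6) = 20.4 h for femoral block. At waits of that order most windows reach the 12 h cap, which corresponds to the upper rows of the table. For PENG the same sum gives 22.67/(3.00/6) = 45.3 h, a sign that the constant-rate model may not fit. If use rises with time, the implied waits are shorter.

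**5. Whether the audit shows the bias.** PENG was lower by 53% (v fascia iliaca) and 67% (v femoral) over 0-6 h, but by 13% and 27% over the whole pre-operative period. Against fascia iliaca block the absolute gap hardly moves: 6.38 − 3.00 = 3.38 mg, and 26.15 − 22.67 = 3.48 mg. Opioid after 6 h is similar in all three groups: 19.67, 19.77 and 21.80 mg (PENG, fascia iliaca, femoral). The percentage shrinks mainly because a similar later amount is added to each group. That is dilution, perhaps with blocks wearing off, and says nothing about unequal observation.

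**6. Why a single whole-window rate is not enough.** Suppose use is 0.5 mg/h in 0-6 h (PENG audit mean, 3.00/6) and 1.5 mg/h in 6-12 h (assumed). A patient leaving at 6 h shows 0.5 mg/h; one observed for 12 h shows (3 + 9)/12 = 1.0 mg/h. The early leaver still looks better, whereas within each interval the rates agree.

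**The case against.** The strongest reply is that the protocol fixes only a collection window and a unit. It does not say that unadjusted totals will be compared, and a statistical analysis plan, not shown here, could use a rate or an offset. A reader might infer that the protocol commits to testing raw totals; it does not, since it names no test at all for this outcome. What remains is that the outcome as defined is a milligram amount over unequal times, and nothing in the protocol puts patients on a common footing. The window itself is reasonable for a pre-operative measure and matches the primary outcome's.

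A second reply is that bias needs block-to-theatre time to differ by block, with enough patients in theatre before 12 h. The documents show neither, and the constant-rate reading of the audit points to waits at which the cap nearly equalises observation. This stands, and it limits the claim about size. It does not remove the point: a long average wait is compatible with a sizeable minority leaving early, and the protocol would not report an imbalance by block.

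A third reply is that mg per hour assumes steady use, and that limiting a 0-6 h comparison to patients still waiting at 6 h selects on an event after the block. Both are right, and the fix has to respect them.

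**Conclusion.** The point holds as a minor one. As defined, opioid requirement mixes consumption with observation time, and with non-randomised block choice any difference in block-to-theatre time within 12 h would pass straight into the comparison. Its size cannot be settled from the protocol. It is negligible if nearly all patients wait beyond 12 h. It is about 11% to 21% only if 10% of one group and 30% to 50% of the other are in theatre at 6 h with a constant rate. The high false-positive rates in the table likewise rest on assumed medians of 8 to 10 h in one group and longer in the other. With equal waits, varying observation time mainly adds noise.

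Two stronger conclusions are tempting. A reader might infer that a spurious opioid saving for PENG is to be expected; the documents give no waiting times by block and no reason to favour either direction. A reader might also take the audit's change from 53-67% to 13-27% as proof of the bias. It is not: the later period there is uncapped, the gap against fascia iliaca block is almost constant in milligrams, and only six patients had PENG (p = 0.5).

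This is a secondary outcome, and no sample size changes.

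**What to change.** In Opioid Requirement, state that blocks will be compared with observed time accounted for: a model for milligrams of oral morphine with log observed time as an offset, or mg per observed hour. Preferably do this by interval, such as 0-6 h and 6-12 h, because the rate may rise as blocks wear off. Patients who reach theatre within an interval should contribute their opioid and their time at risk up to check-in and should not be excluded.

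Report block-to-check-in time, and the proportion observed for the full 12 h, by block. Keep the raw total as description.

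The cost is wording only, since block, drug and check-in times are already needed to apply the existing window. The small downside is that a rate still assumes roughly steady use within each interval. Adjusting for time observed also leaves other confounding from clinician-chosen blocks untouched.

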This audit was unable to demonstrate that PENG, FIB or FNB use less preoperative opioid consumption from time to block to time of operation. These results suggest a possible association between PENG block and reduced opioid consumption. However, these results are not statistically significant and are limited by sample size. This audit demonstrates that a larger study is warranted to assess the effectiveness of PENG blocks in hip fractures.

Pain score documentation was not sufficiently reliable to inform power calculations for this observational study.

Comparison of Nerve Blocks

FEMORAL NERVE BLOCK

ADVANTAGES	DISADVANTAGES
Relatively superficial infiltration.	Close proximity of infiltration to the large femoral vessels can result in inadvertent vascular puncture [24]. This can result in haematoma [34] and increases the risk of LAST (local anaesthetic systemic toxicity) if inadvertent intravascular injection occurs.
Sonographic anatomy familiar to the emergency physician	Requires needle placement directly adjacent to a large motor nerve, which may aggravate the consequences of neural damage [1]. Despite ultrasound guidance the neural tissue is not always well contrasting which increases the risk of intraneural injection.
Direct visualisation of the Femoral Artery (guiding structure for FNB) is easy to achieve in most patients.	In patients with peripheral vascular disease and stents or prostheses of the Femoral artery, the usual anatomy of the Femoral nerve is heavily distorted and standard FNB are impractical.
Usually leads to a motor block of the Quadriceps group of the femur, which prevents spontaneous movement of the injured leg and reduces pain	Unpredictable clinical efficacy. Anaesthesia of only some of the nerve branches of the femoral nerve that supply the anterior hip capsule. No blockade of AON [15]. No blockade of the obturator nerve.

FASCIA ILIACA COMPARTMENT BLOCK

ADVANTAGES	DISADVANTAGES
Well established in clinical practice	Relies on a significant spread of injectate to nerves distant from the point of injection.
Superficial site of infiltration is distant from major vessels, reducing the risk of LAST syndrome or haematoma.	Likely it's efficacy is reliant upon femoral nerve blockade, which may be more reliably achieved by a femoral nerve block.

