Provides anaesthesia to the lateral femoral cutaneous nerve, which innervates the site of skin incision for surgical repair (in lateral approaches only)	Anaesthesia of only some of the nerve branches of the femoral nerve that supply the anterior hip capsule. No blockade of AON [15]. Unlikely to provide blockade of the obturator nerve.
Very low risk for direct neural damage due to remote injection points.	Prolonged onset due to distant injection point and slow spread.

PERICAPSULAR NERVE GROUP BLOCK

A preliminary audit at Lismore Base Hospital performed in May 2019, results show a trend toward reduced pain and morphine requirements n=6. The difference was not statistically significant.

ADVANTAGES	DISADVANTAGES
Utilises bony sonographic anatomy, therefore less variations in performance is expected.	Deeper site of infiltration requires higher technical skills.
Target site contains nerves branches that innervate the anterior hip capsule with greater frequency than FNB or FICB. Only technique that blocks the AON [15, 23]. Closer proximity to obturator nerve branches than other techniques [15]. Makes obturator blockade very likely..	Sonographic anatomy not familiar to emergency physicians. Requires re-training and experience in ultrasound guided needle techniques.
Targets small, distal purely sensory nerves [15, 23]. This should convey a faster onset and more complete blockade. Rapid onset is particularly valuable in the emergency department, where the patient is likely to be moved soon after the block is inserted.	Not well established clinical practice. Quality evidence not yet produced.
Infiltration site is distant from major vasculature, so LAST is less likely. It is distant to any motor nerves which eliminates the risk for major motor nerve damage.	

Aims and Objectives

1. To confirm that the PENGGB is a safe and effective intervention for analgesia of patients presenting to the emergency department with hip fractures.
2. To perform a prospective observational study to assess the PENGGB comparing analgesic efficacy vs current practice of FICB and FNB

Null hypothesis

The PENGGB provides comparable analgesia to patients with fractured neck of femur compared to the FNB and FICB.

Study Design

A prospective observational study.

Current Practice:

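### Aim 1 is to confirm that PENG is safe, but the adverse-event search does not look for the procedural harms on which the protocol bases its safety case

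*Protocol*

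**What the plan says.** The first item under Aims and Objectives in the protocol is "To confirm that the PENGGB is a safe and effective intervention for analgesia of patients presenting to the emergency department with hip fractures". Outcomes and Significance goes further and predicts that the study will probably confirm both efficacy and safety.

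The method for finding harm stands in the Adverse events section, which begins "In an effort to detect the incidence of adverse events, the investigators will" and gives two steps:

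- "Perform a keyword search of the “Continuous Doc” feature of the electronic record, after the patient is discharged from the hospital". The listed keywords are delirium, sedation, constipation (or constipated), aspiration and naloxone.
- "Review the electronic medication chart for use of" two items: naloxone and antibiotics.

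Elsewhere the protocol describes the harms of the blocks themselves. In Comparison of Nerve Blocks, the femoral nerve block table says "Close proximity of infiltration to the large femoral vessels can result in inadvertent vascular puncture" and continues "This can result in haematoma [34] and increases the risk of LAST (local anaesthetic systemic toxicity) if inadvertent intravascular injection occurs". The same table warns of intraneural injection and of needle placement next to a motor nerve, "which may aggravate the consequences of neural damage". The PENG table claims that LAST is less likely and that major motor nerve damage is avoided. The Risk section refers to "local anaesthetic systemic toxicity - which is the most serious adverse event associated with regional anaesthesia" and rests PENG's claimed safety advantage on distance from large vessels and on sparing motor nerves.

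**The concern.** The protocol argues for PENG's safety on one set of harms and searches the record for another. The searched items mostly concern the consequences of opioids and of poorly controlled pain. The harms in the safety argument are those of the needle and of the local anaesthetic.

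What to look for is a data-collection decision, and the Adverse events section fixes it. A separate analysis plan cannot analyse events that were never sought. If the search is run as written and returns few or no block-related events, the result could be reported as fulfilling Aim 1. The protocol expects evidence of safety and efficacy to increase uptake of the technique at its own and other hospitals, and it concedes that PENG is not yet well established. An unsupported safety statement would therefore have consequences.

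**Working it through.** **Step 1. Compare the lists.**

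| Procedural harm named in the protocol | Where named | Among the 5 keywords? | Among the 2 chart items? |
|---|---|---|---|
| Vascular puncture | Comparison of Nerve Blocks (femoral) | No | No |
| Haematoma | Comparison of Nerve Blocks (femoral, fascia iliaca) | No | No |
| LAST | Comparison of Nerve Blocks (all three tables); Risk | No | No |
| Intraneural injection | Comparison of Nerve Blocks (femoral) | No | No |
| Nerve damage | Comparison of Nerve Blocks (all three tables); Risk | No | No |

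None of the five named harms is matched. Data To Be Collected has no block-complication item either: under the nerve block it lists type, content and practitioner experience.

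**Step 2. The number of PENG patients.** The Adverse events section gives no sample size, so the counts come from the pain-score calculations.

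- *Minimum, 74 (25+49).* Inputs: margin 1.5, SD 2.4, one-sided 0.05, power 0.80, ratio 1:2. The normal approximation for the smaller group is (1.645 + 0.842)² × 2.4² × (1 + 1/2) / 1.5² = 23.7, so 24 + 48 = 72. Power from the noncentral t distribution is 0.799 at 24+49 and 0.809 at 25+49. The stated figure reproduces.
- *Early-termination rule, 125 patients with 41 PENG.* Inputs: difference 1.3, SD 2.4, two-sided 0.05, power 0.80, ratio 1:2. (1.960 + 0.842)² × 2.4² × 1.5 / 1.3² = 40.1, so 41; t-based power at 41+84 is 0.805. This also reproduces.
- *Expected at 8 months.* Using the rates in Duration of Data Collection, 15.67 × 0.80 × 8 / 3 = 33.4, or about 33 PENG patients.

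**Step 3. What zero events would show if every event were found.** The one-sided 95% upper limit after 0 events in n patients is 1 − 0.05^(1/n).

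| PENG patients | Upper limit |
|---|---|
| 25 | 11.3% |
| 33 | 8.7% |
| 41 | 7.0% |

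**Step 4. Chance of seeing at least one event.** This is 1 − (1 − p)^n. The protocol gives no event rates, so p is an assumption shown over a range.

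| Assumed true rate | n = 25 | n = 41 |
|---|---|---|
| 0.1% | 2% | 4% |
| 1% | 22% | 34% |
| 5% | 72% | 88% |

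Steps 3 and 4 bear on the word *confirm* in Aim 1. They assume perfect ascertainment and do not measure what the present keyword list would miss.

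**The case against.** A reader might infer that the search has practically no sensitivity for block harms, so that their count will be close to zero whatever happens. The documents do not support this. The ED Data Form (Appendix 4) is completed where the block is placed, and the Limb Observation Chart (Appendix 6) is filled in every 1 to 2 hours on the ward. Neither form is shown, and either might record a complication or a deficit. A listed term such as sedation could also lead a reader of the record to an event by chance. This part of the objection stands: no sensitivity figure can be given. However, the Adverse events section does not name either form as a source, and the change made to the limb chart for this study was to add pain scores and their calculators.

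It is also tempting to call the list purely opioid-related. It is not. Antibiotic use could point to infection, and the protocol links delirium to pain as well as to opioids. These are relevant harms in frail, elderly patients. Block failure, which the hospital's audit counted as an adverse event, is a defined secondary outcome. The list is incomplete rather than misdirected, and the effectiveness half of Aim 1 is untouched.

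Finally, simply adding keywords could do harm. The femoral block table lists quadriceps motor block as a usual effect and counts it as an advantage. An undefined search for leg weakness would therefore record an expected effect as an adverse event, mainly in the comparator group, and would favour PENG. The search also has no stated time window, so loose terms for bleeding or arrhythmia would pick up surgical and comorbid events. Both objections are sound, and the remedy has to meet them.

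**Conclusion.** The concern holds in a limited form. The stated adverse-event method seeks none of the five procedural harms that the protocol names, although Aim 1 is to confirm safety and the protocol expects to do so. A low or zero count under this method would not be evidence of safety on those harms. This rests on the text of the Adverse events section alone; the size of any under-count is unknown while Appendices 4 and 6 are unseen.

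Separately, *confirm* overreaches even with a perfect search: zero events among 25 to 41 PENG patients would remain compatible with a true rate of up to 11.3% or 7.0% respectively. The primary pain comparison is not affected. The absence of a safety comparison from the listed analyses is not part of this point, since an analysis plan may supply it.

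**What to change.** In the Adverse events section, applied identically to all block types:

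- Add search terms for local anaesthetic toxicity or LAST, seizure, cardiac arrest or arrhythmia, vascular puncture, block-site haematoma, and nerve injury.
- Add lipid emulsion to the medication-chart review.
- Count an event only if it is recorded between the block and check-in to the operating theatre, or if the record attributes it to the block.
- Count a motor deficit only if it is recorded as nerve injury or as persisting beyond the expected block effect.
- If Appendix 4 or Appendix 6 already has a field for complications or deficits, name it as a source.

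In Aims and Objectives, replace the aim of confirming safety with that of describing the frequency of block-related adverse events, and bring the prediction in Outcomes and Significance into line.

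The cost is more records to read, including some false hits, and a more modest first aim. The search and chart review are already planned, and no treatment changes.
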